11.3 Securing the Data

The data will be collected by a single nurse coordinator with vascular surgery experience, who has received training on the case report forms developed for use in this study. The coordinator will also be trained to enter information from the case report form into a database set up in SPSS on a password protected PC kept in a locked office. All protected health information on the database will be de-identified. Subjects will be assigned a study number at time of randomization. The case report forms which contain patient identified protected health information will be kept in a locked cabinet within the coordinator's locked office. These will be retained for the required 3 year period following the study and then disposed of per institutional HIPPA policy. A master list of the patient name, DOB, hospital medical record number and study number to allow accurate linking of follow-up data to the index case will also be kept in a locked cabinet in the locked coordinator's office.

11.4 Quality Control of Collected Data – 11.11 Handling and Transmission of Data

All appropriate sections of the case report form (CRF): (See appendix) will be completed by the coordinator, viewed and signed by the principal investigator and entered into the database within two weeks following the subject's discharge for the index procedure. The follow-up forms will be completed within a timely fashion after follow-up.

Study monitors designated by the sponsor will review the information documented in the CRF to verify that the recorded information is consistent with the medical record or other source documents and that input of this information into the data base is accurate. Errors or incomplete data will be rectified. All information will be treated as confidential. The following individuals will have full access to the data: Principal investigator, clinical

coordinator, statistician Co-investigators, vascular technicians, Core Lab personnel and study monitors will have access on an as needed basis.

Table 2. Adverse Event Definitions and Categorizations

Adverse Event	Any undesirable medical occurrences in a subject whether or not it is related to the study device, procedure or study requirements that is identified or worsens during the clinical study	
Major Adverse Event	A primary safety endpoint adverse event defined as Szilagyi Grade III infection of the randomized incision and all-cause mortality	Grade III Szilagyi infection of the randomized incision All-cause mortality
Serious Adverse Event	Any adverse event that results in death, is life threatening, requires > 24 hour in-patient hospitalization, or prolongation of an existing hospitalization, requires intervention to prevent permanent impairment/damage or results in persistent or significant disability/incapacity	Myocardial Infarction Congestive Heart Failure Pulmonary Embolus Respiratory Failure Stroke Cardio/Pulmonary Arrest Thirty day hospital readmission for Grade II or III Szilagyi infection of the randomized incision
Unanticipated Adverse Event	Any serious adverse event leading to injury, illness or death of a subject not previously identified in nature, severity or degree of incidence in this protocol, literature or application (including a supplementary plan or application) that may be directly related to use of the device	

Table 3. Procedure Related Categories for Adverse Events

Procedure Related Adverse Event	AE that have a strong temporal relationship to the procedure and an alternative etiology is unlikely
Probably Procedure Related Adverse Event	AE that have a strong temporal relationship to the procedure and an alternative etiology is less likely than the potential relationship to the procedure
Probably–Not Procedure Related Adverse Event	AE that have minimal or no temporal relationship to the procedure and/or a more than likely alternative etiology
Not Procedure –Related Adverse Event	AE is due to the underlying disease state or concomitant medication or therapy and not caused by the procedure

Criteria for MAE and SAE

Serious Infection-	Grade III Sziglgyi infection of the randomized incision
Myocardial Infarction-	Per the ESC/ACC definition for acute, evolving or recent MI Typical rise and gradual fall of Troponin or more rapid rise and fall of (CK-MB) biomarkers or myocardial necrosis with at least one of the following: 
 • Ischemic symptoms • Development of pathologic Q wave on ECG • ECG changes indicative of ischemia (ST segment elevation or depression) or coronary artery intervention (ie: coronary angioplasty • Pathologic findings of an acute MI
Congestive Heart Failure-	New or worsening shortness of breath confirmed by chest x-ray findings consistent with CHF and/or requiring unscheduled dialysis or fluid restriction
Cerebrovascular Accident-	A neurologic deficit lasting more than 24 hours, or lasting less than 24 hours with a brain imaging study showing infarction.
Pulmonary Embolus-	Embolus in the pulmonary vascular documented by CT findings
Respiratory Failure-	Respiratory difficult requiring intubation
Cardio-Pulmonary Arrest-	Loss of pulse and respiration. Need for cardio-pulmonary resuscitation to prevent impending death

Interim analysis will be performed of the primary and secondary endpoints after half of the subjects are enrolled and again when all subjects are enrolled. Anova will be used to determine differences in infection rates between the two treatment arms. The PI will verbally communicate the findings to Acelyty with recommendations to continue, stop the study or make changes to the protocol if additional patients are needed to achieve statistical significance. These will be provided in writing within 4 weeks.

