7.0 Study Timelines

7.1 Duration of subject's participation

Subjects will be evaluated throughout hospitalization including the day of discharge, and at 30 days (25 - 40) following surgery. This will include clinical assessment (Szilagyi Scale) of the groin incision for presence of infection, need/use of antibiotics for groin

incision infection and need for visiting nurse home visits or surgeon office visit prior to scheduled follow-up to treat infection of the groin incision randomized to treatment.

[figure not shown]

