 - AE Evaluation: any infection of the randomized incision or other major postoperative morbidity related or unrelated to the surgical procedure/ wound treatment which may include but is not limited to: MI, CHF, CVA, Respiratory distress/failure, renal failure requiring dialysis, re-intervention for any reason, thrombosis, embolization, amputation, blood loss requiring treatment.

Table1. Study Assessment Requirements

Assessment Schedule (Time-Frame Window)	Baseline ≤45 days prior Labs ≤ 30 days prior	Procedure	Daily While Hospitalized	Day of Discharge	30 Day Follow-up 25-40 Days
Medical History	X				
Physical Exam	X				
Concomitant Medication Use	X	X	X	X	X
Laboratory Testing	X				
Clinical Status Evaluation	X	X	X	X	X
With ABI	X		X _(x1)	X	X
Adverse Event Evaluation		X	X	X	X

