19.3 Location of Research procedures

Research procedures will be completed in the following areas

- Surgeon's exam room, patient hospital room or other private room in the hospital
Patients may be screened for eligibility, consent obtained and randomized to a study arm in the surgeon's office, patient hospital room or other private room in the hospital.
- Operating Room

- Prevena (3 units) and Dermabond are both readily available in the OR supply area. The coordinator will ensure that there continues to be an adequate supply to allow for randomization. Both products are also used for other procedures, both vascular and other surgical interventions.
- The Clinical coordinator's office, participating surgeon's office, medical record department, hospital surgical unit
These areas may be used for collecting and in-putting data.

The aforementioned precautions will be used to assure patient confidentiality

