Class IV	Frequently bed or chair ridden for most of the day and is too weak and short of breath to do simple activities

Death: Termination of Life

Device Malfunction: Defined as a malfunction in the Prevena Incision Management System such that it did not perform its intended function when used in accordance with the *Instructions for Use*.

Device-Relatedness Categories of Adverse Events:

Device Related Adverse Event	AE that have a strong temporal relationship to the presence or performance of the device/system and an alternative etiology is highly unlikely
Probably Device Related Adverse Event	AE that have a strong temporal relationship to the presence or performance of the device/system and an alternative etiology is less likely than the potential relationship to the device/system
Probably–Not Device Related Adverse Event	AE that have minimal or no temporal relationship to the presence or performance of the device/system and/or a more than likely alternative etiology exists
Not Procedure –Related Adverse Event	AE is due to the underlying disease state or concomitant medication or therapy and not caused by the device/system

Device Success: Ability to deploy the Prevena Incision Management System as intended at the treatment site.

Diabetes (History of): Defined as subjects who have been diagnosed with either Type I or Type II diabetes and are currently diet controlled, taking oral hypoglycemic or insulin.

Discharge: The time-point in which the subject is released from the admitting hospital, transferred to another facility or expired.

Dissection: Intimal disruption of the vessel wall.

Embolus/Embolization: Obstruction of a blood vessel by a foreign substance (air, plaque debris or blood clot).

Emergent Surgical Revascularization: Surgery performed on an urgent or emergent basis.

Enrollment: The subject is enrolled after he/she has signed the informed consent and has been determined to meet all the inclusion criteria and no exclusion criteria.

Fever: An increase in internal body temperature to levels above normal: (37° C or 98.6° F).

Hematoma: Localized mass of extravasated blood.

Hemorrhage: Bleeding requiring hospitalization, repeat procedure, operation or Transfusion.

Hypertension: Increase in the systolic blood pressure over 140 mm Hg or a diastolic blood pressure above 90 mm Hg.

Hypotension: Fall in systolic blood pressure that requires treatment with vasopressors, inotropic agents or fluid resuscitation.

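### Both between-arm looks are triggered by enrolment, with no follow-up condition or data cut-off, although the endpoint is a 30-day postoperative outcome

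*Combined protocol and SAP*

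**What the plan says.** The interim analysis paragraph follows the criteria for major and serious adverse events and stands just before section 13.0. It schedules analysis of the primary and secondary endpoints "after half of the subjects are enrolled and again when all subjects are enrolled". It is a comparison between arms: "Anova will be used to determine differences in infection rates between the two treatment arms". The result goes to the sponsor with "recommendations to continue, stop the study or make changes to the protocol if additional patients are needed to achieve statistical significance".

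Section 32.0 fixes what enrolment means: "The subject is enrolled after he/she has signed the informed consent and has been determined to meet all the inclusion criteria", with no exclusion criterion met. Surgery is not part of the definition. Section 19.3 allows patients to be screened, "consent obtained and randomized to a study arm in the surgeon's office", as well as in a hospital room. Table 1 in section 9.2 heads its first column "Baseline ≤45 days prior".

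The outcome comes later. Section 8.1 bases the primary effectiveness endpoint on healing over 30 days, with any infection or failure to heal in that time counting. Section 7.1 places the last assessment "at 30 days (25 - 40) following surgery". The cost endpoint in section 8.1 includes 30-day readmission for infection of the randomized wound.

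No section makes either look wait for follow-up, sets a data cut-off, or says how patients with a pending assessment are handled.

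**The concern.** The trigger counts patients at a point before surgery, but the quantity analysed is known only some weeks after surgery. When the 70th or 140th patient enrols, the most recent patients cannot yet have a 30-day outcome, and some may not have been operated on.

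The recommendation to continue, stop or change the study would then rest on incomplete outcomes. Leaving pending patients out costs precision. Carrying them at their in-hospital grade would count an infection that appears after discharge as no infection, and would omit its readmission cost. The synopsis's secondary endpoints (readmission cost, antibiotics at discharge, home and office visits) are largely about care after discharge, so these late events matter. Too few events at a look could suggest no effect, or a need for more patients, merely because follow-up was unfinished.

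This point concerns the trigger only. Error control across the looks, the choice of test and access to results are separate; correcting them would leave the trigger as it is.

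**Working it through.** **The plan's own figure.** Section 9.13 states power 0.88 with 70 + 70 patients and type I error 0.05, for grade probabilities 0.90/0.08/0.019/0.001 (Prevena) and 0.70/0.16/0.11/0.03 (Dermabond). Simulating those vectors in a single stratum, two-sided (the plan does not state sidedness), gives 0.889 for the proportional-odds score test (10,000 runs), 0.882 for the likelihood-ratio test and 0.866 for the Wald test (3,000 runs each). The stated figure is reproduced. It presumes that all 140 endpoints are observed.

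**Inputs for the pending count.**
- Patients: 140, with looks at 70 and 140 (section 4.1 and the interim paragraph).
- Accrual: 12 months (section 7.2), or 21 months with the longest extension in section 20.3 (12 + 9). Even accrual is an assumption.
- Surgery to assessment: 25 to 40 days (section 7.1).
- Enrolment to surgery: not given. The base case assumes 0 days. The upper bound assumes 45 days, borrowed from the baseline window in Table 1.

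**Formula.** Pending patients = accrual rate × days from enrolment to assessment.

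Rates: 140 / 365 = 0.3836 per day over 12 months; 140 / 638.75 = 0.2192 per day over 21 months.

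| Accrual | Lag (days) | Pending | Share of 70 | Share of 140 |
|---|---|---|---|---|
| 12 months | 0 + 25 | 9.6 | 14% | 7% |
| 12 months | 0 + 30 | 11.5 | 16% | 8% |
| 12 months | 0 + 40 | 15.3 | 22% | 11% |
| 12 months | 45 + 40 | 32.6 | 47% | 23% |
| 21 months | 0 + 25 | 5.5 | 8% | 4% |
| 21 months | 0 + 40 | 8.8 | 13% | 6% |
| 21 months | 45 + 40 | 18.6 | 27% | 13% |

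In the 12-month row with the 45-day gap, 0.3836 × 45 = 17.3 of the pending patients would not yet have had surgery.

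**If pending patients are left out.** Single-look power was simulated with the score test at the plan's rates, two-sided 0.05, with complete cases rounded so that the arms are equal. The proportional-odds test stands in for the test named in the interim paragraph.

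| | All counted patients complete | 30-day lag | 85-day lag |
|---|---|---|---|
| Look 1 | 70: 0.60 | 58: 0.52 | 38: 0.36 |
| Look 2 | 140: 0.88-0.89 | 128: 0.85 | 108: 0.80 |

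The last two columns use 12-month accrual. For example, 70 − 11.5 is about 58 and 140 − 11.5 is about 128.

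**If pending patients are carried at their in-hospital grade.** Infection rates and readmission costs are understated. The size cannot be computed, because the documents do not give the share of infections that arise after discharge.

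**The case against.** The strongest reply is that silence is being read as a rule. The paragraph names a milestone but no data cut-off and no analysis set, and its wording does not forbid waiting for follow-up. This stands in part: the pending counts hold only if the data are cut at the enrolment milestone. But nothing requires anyone to wait, and the only condition stated is enrolment.

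Three stronger readings are tempting, and the documents do not support them.

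- A reader might infer that the trial's final result will lack outcomes. Section 8.1 follows every randomized patient to 30 days, section 9.12 specifies an intent-to-treat ordinal analysis, and section 20.3 allots 3 to 6 months for analysis, write-up and closure. A complete final analysis is compatible with all of this, although the plan does not clearly separate it from the second look.
- A reader might take nearly half the first-look patients as the expected shortfall. That needs every recent patient to wait 45 days for surgery and attend on day 40. The 45 days is a window for baseline assessments, and section 9.2 bases these on data available at enrolment, so they may predate it. Sections 19.2 and 19.3 also allow recruitment from the daily operating room schedule and consent in the hospital room, where the gap may be short.
- A reader might infer that the plan counts pending patients as uninfected. It does not say so. Patients already operated on have provisional grades from daily inpatient checks, but no rule says how these are used. If pending patients are simply left out, 1:1 blocked allocation gives no reason to expect imbalance between arms; the loss is precision.

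It is also fair that the first look is weak in any case (power about 0.60 with all 70 complete), and that once all 140 are enrolled, stopping accrual is moot and mainly the question of adding patients remains.

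**Conclusion.** The concern holds as a defect in the stated trigger: both looks are set by an event before surgery, with no follow-up condition and no cut-off, for an endpoint that needs 30 days after surgery.

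If the looks are run at the enrolment milestones, the base case (even 12-month accrual, same-day surgery) leaves about 10 to 15 patients pending. That is appreciable at the first look and modest at the second. The figure of about 33 is an upper bound resting on the assumed 45-day gap. Accrual over 21 months gives about 5 to 19 across the whole range of lags. Leaving pending patients out has a moderate effect on power in the base case, about 8 points at the first look and 3 at the second. The effect of carrying them forward is a downward bias of unknown size.

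The harm falls on the recommendation to stop, continue or add patients, chiefly at the first look. It should be corrected, but it does not by itself undermine a complete final analysis.

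**What to change.** Reword the interim paragraph so that each look is made after the first 70 randomized subjects, and then all randomized subjects, have completed the 30-day (25-40) assessment or have died, withdrawn, or been declared lost to follow-up under section 13.4. Restrict each look to that cohort. Death and withdrawal must be named: a trigger that recognised only completed visits and loss to follow-up could be blocked by a single death or withdrawal. If the second look is the final analysis, say so; if not, state when the final analysis takes place.

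The cost is one sentence and a delay of roughly 1 to 3 months per look (25 to 85 days). While the first 70 complete follow-up, about 10 to 15 further patients (at most about 33) would be enrolled before the first look on 12-month accrual, so any recommendation to stop would come after about 80 to 85 enrolments (at most about 103). There are no extra visits and no change to the planned 140.

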9.0 Procedures Involved

9.1 Study Design

This is a prospective multicenter randomized double arm study to evaluate the prevention of groin wound infections in patients undergoing vascular surgery which requires ≥ 8 cm groin incision.

9.11 Randomization Plan:

We will employ a 1:1 randomization to either Prevena or Dermabond using a stratified blocked randomization plan with strata determined as a single incision or a bilateral incision with sequences of random block sizes of 4 or 8. Within the bilateral incision strata, one incision will be randomly chosen relative to defining a single endpoint measure, with site of incision essentially serving as a secondary substratum.

9.12 Statistical Analysis Plan Outline:

Primary Endpoint

The primary endpoint for this trial will be Szilagyi wound infection grade quantified on an ordinal scale (none, grade I: infection contained to the dermus, grade II: infection extending into the subcutaneous tissue but the arterial graft is not involved, grade III: infection of the arterial graft or native vessel underlying the incision). The primary analysis will be intent to treat and carried forth using an ordinal regression model with a stratified likelihood accounting for the primary randomization strata (incision number) and binary indicator variable for treatment arm with the primary test of treatment efficacy being the proportional odds different from 1. In the event of sparse data at the higher grades of infection (<2% at grade III), categories II and III will be combined. For the bilateral incision strata, the primary endpoint will be determined by randomly choosing a single incision as determined within the randomization scheme.

Secondary Endpoint

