The secondary endpoint will be a comparison of cost of treatment between the two arms and will be considered an exploratory analysis. We will utilize regression approaches to account for potential selection bias and censored cost endpoints. We have completed a preliminary appraisal of the additional per patient hospital costs (dispersed over the entire sample) for treating groin wound infections using the following assumptions. The associated wound infection rate for Prevena would be 6%.³ Groin wound infections for Prevena and Dermabond would require comparable care. Although lower wound severity grades have been reported for Prevena³ which could potentially decrease the complexity, duration and cost of subsequent treatment of wound infection for this group, the finding was not statistically significant.³ Therefore, we projected that treatment of groin wound infection in both groups would include an increased 10 day hospital length of stay,¹ seven days of IV antibiotics, daily CBC with or without differential and 2 cultures. We have estimated that the additional per patient cost of treating groin wounds if Prevena were used preemptively (\$935- \$1,114) would be similar to Dermabond (\$869- \$1,168) if the incidence of wound infection with Dermabond is $\leq 10\%$.

9.13 Sample size rationale:

Given $N=140=70+70$ total subjects and setting the Type I error rate = 0.05, we will have the power of 0.88 to detect a proportional odds of 4.9 different from 1. For our calculations, we assumed a probability vector for the ordinal scale (none, grade I, grade II, grade III) of (0.90, 0.08, 0.019, 0.001) for the Prevena treatment arm and (0.70, 0.16, 0.11, 0.03) for the Dermabond arm respectively. The power estimate was carried forth using 10,000 Monte Carlo simulations. This volume should be easily attainable over a 12 month period because on average 484 lower extremity revascularizations and 100 Abdominal Aortic Aneurysm Repairs are performed annually at Kaleida Health. While most of these procedures (85%) are completed by endovascular approach, access by groin cutdown is necessary in 25% of EVAR and 10% of EVI in addition to the planned open lower extremity revascularizations, which should allow for adequate numbers. SPSS 22 will be used to perform the statistical analysis.

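### The looks that drive the continue/stop/change recommendation are tied to an ANOVA on undefined infection rates, not to the stratified ordinal test that the plan makes primary and powers

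*Combined protocol and SAP*

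**What the plan says.** Section 9.12, repeated under 11.1/11.2, sets the endpoint: "The primary endpoint for this trial will be Szilagyi wound infection grade quantified on an ordinal scale". The intent-to-treat primary analysis is an "ordinal regression model with a stratified likelihood accounting for the primary randomization strata (incision number) and binary indicator variable for treatment arm", and the test of efficacy is whether the proportional odds differ from 1. Grades II and III are merged if grade III is below 2%.

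Section 9.13, also repeated under 11.1/11.2, states for 70 per arm and Type I error 0.05 that "we will have the power of 0.88 to detect a proportional odds of 4.9 different from 1". It gives grade probabilities for each arm.

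The interim paragraph follows the table of MAE and SAE criteria and precedes section 13.0. It says: "Interim analysis will be performed of the primary and secondary endpoints after half of the subjects are enrolled and again when all subjects are enrolled". The next sentence names the method: "Anova will be used to determine differences in infection rates between the two treatment arms". The principal investigator then reports the findings to the sponsor with "recommendations to continue, stop the study or make changes to the protocol if additional patients are needed to achieve statistical significance". The paragraph does not mention the ordinal model, the incision-number strata or the merging rule. It does not define infection rates or say how the ANOVA relates to the primary test.

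**The concern.** One endpoint has two named methods, and the one named where trial-level decisions are made is not the one the trial was designed around. If the two disagree at a look, nothing says which one the recommendation follows.

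The ANOVA is also under-specified. It could be run on any infection (yes/no) or on grade scored 0 to 3, and these behave differently. With the ordinal model there are then three candidate analyses at each look, and the choice could be made after seeing the data. At stake is the integrity of a recommendation that may stop the study or enlarge it.

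**Working it through.** **Inputs.** From section 9.13: 70 per arm, alpha 0.05, and probabilities for none/I/II/III of (0.90, 0.08, 0.019, 0.001) for Prevena and (0.70, 0.16, 0.11, 0.03) for Dermabond. From the interim paragraph: looks at about 70 subjects (35 per arm) and at 140.

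**Assumptions.** The paragraph gives no decision threshold, so two-sided 0.05 is used at each look. All enrolled subjects are taken to have outcome data. The bilateral share is not given, so the comparison of tests is unstratified. A stratified score test with assumed shares of 20%, 35% and 50% gave power 0.88 to 0.90, so this matters little.

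**1. The plan's own figure.** With 10,000 simulated trials, the proportional-odds model has power 0.884 (Wald) or 0.896 (likelihood ratio). With the merging rule the values are 0.882 and 0.895. The stated 0.88 is reproduced.

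**2. What each ANOVA compares.** With n per arm, arm means m₁ and m₂, and pooled within-arm mean square MSE, F = (n/2)(m₁ − m₂)²/MSE on 1 and 2n − 2 degrees of freedom.
- Any infection: 1 − 0.90 = 0.10 against 1 − 0.70 = 0.30, a difference of 0.20.
- Grade 0 to 3: 0.08 + 2(0.019) + 3(0.001) = 0.121 against 0.16 + 2(0.11) + 3(0.03) = 0.47, a difference of 0.349.

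The planning odds ratios grow with severity:
- Any infection: (0.30/0.70)/(0.10/0.90) = 3.86.
- Grade II or worse: (0.14/0.86)/(0.02/0.98) = 7.98.
- Grade III: (0.03/0.97)/(0.001/0.999) = 30.9.

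Scoring by grade therefore gains power, and reducing to yes/no loses some.

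**3. Power at 70 per arm.**

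| Test | Power |
|---|---|
| Ordinal, score test (Wilcoxon with ties) | 0.887 |
| ANOVA, any infection | 0.863 |
| ANOVA, grade 0 to 3 | 0.927 |

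**4. Opposite verdicts at 0.05 under the planning probabilities.** The Wald and likelihood-ratio versions use the merging rule.

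| Ordinal test | Per arm | v ANOVA, any infection | v ANOVA, grade |
|---|---|---|---|
| Score | 70 | 2.7% | 5.3% |
| Wald | 70 | 2.2% | 5.8% |
| Likelihood ratio | 70 | 2.9% | 5.0% |
| Score | 35 | 4.5% | 9.3% |
| Wald | 35 | 6.8% | 14.0% |
| Likelihood ratio | 35 | 5.4% | 8.5% |

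The direction depends on the outcome chosen. At 70 per arm, disagreements with the any-infection ANOVA nearly all favour the ordinal test (Wald: 1.9% against 0.3%). Disagreements with the grade ANOVA nearly all favour ANOVA (Wald: 5.3% against 0.5%).

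**5. No effect, 70 per arm.** Both arms were given the Prevena vector, the Dermabond vector or their average. With the score test, at least one of the two tests is significant in about 5.2 to 6.0% of trials (any-infection ANOVA) or 5.9 to 6.4% (grade ANOVA). The Wald and likelihood-ratio versions stay within 5.3 to 5.9% and 6.0 to 6.7%.

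**The case against.** Four arguments weaken the point, and each rules out a stronger reading.

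- A reader might infer that nothing decides the final claim. That is not so. Section 9.12 and its repeat under 11.1/11.2 both name the proportional-odds test as the test of efficacy, and the ANOVA is nowhere called primary. The gap concerns the recommendation.
- A reader might infer that the ANOVA discards grade and lacks the planned power. The text says only infection rates, and the hypothesis in section 1.2 speaks of rates graded by the Szilagyi score. On the grade reading ANOVA has more power than the ordinal test, not less. Nor does silence about strata prove that they would be left out, since an ANOVA can carry a stratum factor.
- A reader might see the second look as a rival final analysis. The paragraph calls it interim and times it at full enrolment. The follow-up visit falls at 25 to 40 days, so the last subjects may lack outcomes at that point.
- The paragraph covers the primary endpoint, which is ordinal, so it does not expressly exclude the ordinal model at those looks.

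All four stand as limits. None removes the inconsistency: ANOVA is the only method the paragraph names, it is not marked as supportive, and the recommendation follows directly after it.

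**Conclusion.** The inconsistency is real and should be corrected, but its numerical effect is modest. Under the planning probabilities, opposite verdicts occur in about 2 to 6% of trials at full size and about 4.5 to 14% at half size, depending on how infection rates are defined and which form of the ordinal test is used. With no effect, the freedom to choose between the two tests adds at most about 1.7 percentage points to a nominal 5% at full size. The stated power of 0.88 is sound for the ordinal test.

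These figures assume a 0.05 threshold at each look, complete outcomes and the section 9.13 probabilities. They cover only the choice of test. Two unadjusted 0.05 looks with a single test give about 8.3% Type I error by normal approximation. That is a separate issue and lends no weight to this one.

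**What to change.** Replace the ANOVA sentence with a statement to this effect: any look at the primary endpoint uses the stratified ordinal regression of section 9.12 with its rule for merging grades II and III, and this test alone governs both the recommendation and the final efficacy claim. Report any-infection rates by arm descriptively, as a risk difference with a 95% confidence interval.

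If the ANOVA is to be kept, a weaker alternative is to define infection rates, label the ANOVA supportive and state that the ordinal test governs.

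The cost is about one sentence of protocol text, with no extra patients or data. The stated power of 0.88 is unchanged, apart from any adjustment made for the interim look, which has to be settled separately.
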